As a contingency, exercise training may be done remotely. At the PI, research team member, or study physician's discretion, participants may conduct exercise training at their residence, local gym, or other appropriate facility. During these training sessions, a study team member will communicate with the participant prior to the session and discuss the goals and training plan. More specifically, a team member will discuss where the session is to occur, the duration of the session, mode of exercise, and exercise intensity. During the session, a team member may monitor exercise via telephone or video chat (e.g., zoom). Exercise intensity is monitored via a HR monitor. Each participant wears a Polar HR monitor watch for the duration of the study and is familiarized with its use. If a remote session is to occur, the participant will be sent home with a heart rate strap that communicates with the watch to give HR feedback (i.e., via mail, during visit to the lab, or meeting a local establishment, etc). HR is digitally recorded and downloaded as described elsewhere (another form of monitoring exercise).

Standard Care

All subjects will receive standard care for diabetes management as directed by their individual physician and diabetes health care team according to American Diabetes Association, Standards of Medical Care in Diabetes position statement, 2018 [33]. All newly diagnosed subjects with type 2 diabetes will be encouraged to receive Diabetes Self-Management Education. In addition, both groups will be given a wrist worn device during the intervention and trained in their use to track physical activity patterns. Subjects will meet approximately twice monthly with the study team to download accelerometer data.

Reasons for Withdrawal

Participants are free to withdraw their consent and discontinue participation at any time. We do not anticipate participant withdrawal due to study-related reasons as similar exercise training interventions have been taking place for decades with high levels of adherence. Additionally, we have extensive experience managing clinical trials in the proposed population [26, 30, 34, 35]. However, we recognize participants interests, health, and schedules may change. The research team's best effort will be made to accommodate the participants needs and minimize attrition. The following are potential reasons for withdrawal:

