- **Time Commitment**: Some participants may find the time commitment associated with this study too burdensome for their schedule. The study coordinator will discuss this time commitment prior to enrollment.
- Schedule Conflicts: Some participants may find it difficult to determine times they are available to come in for study visits. The study coordinator will also discuss preferred visit start times prior to enrollment to limit potential schedule conflicts.
- **Discomfort:** Participants may experience discomfort during blood and tissue sampling procedures and wish to discontinue the study. Prior to enrollment, the study coordinator will discuss all procedures and answer any questions participants may have concerning sampling procedures.
- **Unforeseen Reasons:** There may be other reasons participants may withdrawal from the research study that are unknown at this time.

Handling of Withdrawals

The participants right to withdraw from the study will be respected and will occur within the timeframe they request. In the event of a participant withdrawal, samples and data collected during their participation will be stored for future use or destroyed, based on the participants request.

Termination of Study

The research staff reserves the right to suspend/terminate subject's participation in this study at any time. This decision will be communicated to the participant and a reasonable effort will be made to mitigate/avoid this outcome. Potential study suspension/termination reasons include:

- **Ineligibility**: The subject's eligibility changes during the study
- Safety: The research has become harmful to the participant
- **Health**: The subject's health condition changes and requires treatment which affects the study outcomes
- **Incompliance**: Subject fails to follow the study guidelines
- Cancelation: The research study is canceled or suspended

Accountability Procedures for the Study Intervention

The research team will communicate internally weekly to discuss study progress and ensure all objectives and guidelines are met. From a participant perspective, agreement to enroll in the study will necessitate adherence to all study guidelines. The research staff will have regular contact (approximately 5 days/week) with subjects in the Aerobic Exercise group and will meet approximately twice monthly with the control group to monitor habits and study progress. We have found these interactions are indispensable for study adherence.

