Concomitant Medications

[figure not shown]
Subjects participating in this study will be diagnosed with T2DM and therefore have unique medical needs. In addition to the screening provided in this study, each participant will be encouraged follow their personal physician's guidance. Prior to and during the intervention period, all medication use, dose and frequency will be documented

Assessment of Subject Compliance with Study Intervention

Subject compliance will be regularly assessed and documented by the research team. Participants enrolled in the AE group will have contact with the research team approximately 5 days per week and the Control group will have contact with the research team approximately twice per month. Compliance will be determined through routine personal communication and primarily evaluated based on exercise training attendance (Aerobic Exercise group only), physical activity tracking, and dietary monitoring. Subjects in the Aerobic Exercise group are expected to complete \geq 80% of the training sessions over the course of the 12 weeks.

STUDY SCHEDULE AND PROCEDURES

Figure 3 provides a brief study summary of the study schedule. This study is composed of initial subject screening and enrollment based on established inclusion and exclusion criteria and randomization to 12 weeks of Aerobic Exercise training or Control Period (both including established Standard Care practices). Participants will all complete the same baseline testing and final study visit testing. Subjects randomized to the AE group will also undergo follow-up testing at weeks 4 and 8 (\pm 1 week) to adjust exercise training parameters. All testing will occur at the Michigan Clinical Research Unit (MCRU), Michigan Nutrition Obesity Research Center (NORC), Domino Farms, Frankel Cardiovascular Center (CVC), and/or Central Campus Recreation Building (or other University recreation building) and based on subject schedules, will include a total of approximately 7 visits.

Scheduling Flexibility

Due to limitations of the subject's schedule, study team, experimental approach, and/or clinic availability, some procedures may be excluded or adjusted from any given visit. Excluded or adjusted procedures will be at the discretion of the PI or Co-I and will not be considered a protocol deviation.

Subject Screening

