All subjects will return for follow-up testing at approximately weeks 4 and 8. Each subject will have a blood draw (~20 ml) and the AE group will also complete a VO₂max test to adjust target HR for the training protocol.

Final Study Visit Testing

The final study visit at MCRU or Domino Farms will include the same testing procedures for both groups that were completed during baseline testing (i.e., body

composition assessment, cognitive assessment, OGTT, measurement of insulin sensitivity). In addition, all subjects will undergo an acute aerobic exercise bout (treadmill walking) coupled with microdialysis and muscle biopsies.

Total Study Tissue Sampling

Table 1 outlines the approximate amount tissue to be collected during the study. Tissue samples (blood, urine, and muscle) will be obtained during the screening and/or baseline (before the 3 month AE intervention or control period), follow-up visits, and final study visits (after the 3 month AE intervention or control period) time points. Therefore, these time points will be separated by >3 months. In addition, participants in this study will be overweight or obese and have a body weight > 110 lb. Thus, the proposed blood draws are acceptable by University of Michigan IRBMED guidelines.

Table 1		
Time point	Blood	Muscle
Screening Visit		
Both groups	20 ml	-
Baseline Visit		
AE group	280 ml	400 mg
Control group	280 ml	400 mg
Initial Exercise Bout		
AE group	80 ml	-
Control group	80 ml	-
Follow-up Visits		
Both groups	40 ml	-
Final Visit		
AE group	280 ml	400 mg
Control group	280 ml	400 mg
AE group total	~700 ml	~800 mg
Control group total	~700 ml	~800 mg

Sample Preparation, Storage, and Shipping

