Study samples and resultant data will not contain personal identifying information. Each subject will receive a unique study identifier and samples will be appropriately labeled based on the testing procedure and sample type. All source document data will be kept in a locked file cabinet and converted to electronic data. All electronic data will be safe-guarded by password protection on a University of Michigan server. Sample preparation will be completed by the research team and/or MCRU/NORC staff during each procedure. This includes processing of muscle biopsy, blood, and microdialysis samples. Samples will be stored in a -80 °C freezer. Handling and shipping of study samples will only occur by the trained research staff as directed by Michigan Occupational Safety and Health Act (MIOSHA) and Occupational Safety and Health Administration (OSHA) guidelines.

Assessment of Safety

The risk to benefit ratio for this study is excellent. Overall, the risks are minor with the information gained on the impact of exercise on diabetes invaluable. Safety will be regularly monitored through personal communication, observation, and documentation. Each individual involved in this study will be encouraged to communicate needs and any potential issues that arise.

Adverse Events

Members of the research team will be present for all components of the study to monitor safety. Additionally, the research team will communicate weekly for review of safety and data collection. In the situation of an adverse event, the event will be immediately managed an IRBMED Adverse Event Report Form will be sent to the appropriate clinical site and Institutional Review Board in a timely manner. This report will include a full description of the event, including the relationship of the incident to the test procedure.

Potential Adverse Events and Mitigation Strategies

Breach of Confidentiality: There is a potential for breach of confidentiality. Study samples and resultant data will not contain personal identifying information. Each sample will be stored with a unique code. All source document data will be kept in a locked file cabinet and converted to electronic data. All electronic data will be safe-guarded by password protection and encryption on a University of Michigan server.

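### Adverse events are found through unstructured contact that is about 7 to 11 times more frequent in the exercise arm, so minor events between shared visits risk being under-recorded in controls

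*Combined protocol and SAP*

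**What the plan says.** The method of finding events is stated under Assessment of Safety: "Safety will be regularly monitored through personal communication, observation, and documentation". The next sentence adds: "Each individual involved in this study will be encouraged to communicate needs and any potential issues that arise". Neither that section nor Adverse Events gives a standard question, checklist, recall window or assessment schedule.

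Contact is set out under Assessment of Subject Compliance with Study Intervention. For the exercise arm: "Participants enrolled in the AE group will have contact with the research team approximately 5 days per week". For controls: "the Control group will have contact with the research team approximately twice per month". Accountability Procedures for the Study Intervention gives the purpose of the control contacts: the team "will meet approximately twice monthly with the control group to monitor habits and study progress". Adverse events are not named there.

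Aerobic Exercise Training adds surveillance in one arm only: foot checks for ulcers and blisters, and heart rate and blood pressure recorded at every session.

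The arms also share contact points. Standard Care, where both groups receive the wrist device, says: "Subjects will meet approximately twice monthly with the study team to download accelerometer data". Follow-up Testing says: "All subjects will return for follow-up testing at approximately weeks 4 and 8". Both arms have the final visit and next-day follow-up after every biopsy. Concomitant Medications requires drugs, doses and frequency to be recorded before and during the intervention, without distinction by arm.

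**The concern.** When events surface through ordinary conversation and observation, the number recorded depends on how often staff see the participant as well as on how often events occur. Here the frequency of contact is fixed by the randomised arm. A sore knee, a dizzy spell or a blister has about five chances a week to be noticed in the exercise arm, but may have healed and been forgotten before a control participant's next meeting. The exercise arm also has two ways of finding events, foot inspection and session blood pressures, with no counterpart in controls between visits.

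At stake is the reading of any description of events by arm, whether for the data safety monitor, the Institutional Review Board or a publication. Equal true rates of minor events could look like an excess caused by exercise, and minor events in controls could go unseen. The primary and secondary outcomes are not directly affected.

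**Working it through.** The plan states no figure for event capture, so there is none to reproduce. The check has two parts.

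**1. Contact frequency**

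Inputs: 5 contacts a week (exercise) and 2 a month (control), from the compliance section; 12 weeks, from Intervention Description; at least 80% of sessions expected to be completed, from the compliance section; two common visits at weeks 4 and 8, from Follow-up Testing.

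- Exercise, full attendance: 5 × 12 = 60.
- Control, calendar months: 2 × 12 × 12/52 = 5.54. With 4-week months: 2 × 3 = 6.
- Ratio: 60/5.54 = 10.8, or 60/6 = 10.0. The 10.8 is the same for 11 or 13 weeks, because both counts scale with duration.
- At 80% attendance: 0.8 × 60 = 48, and 48/5.54 = 8.7.
- Weeks 4 and 8 added to both arms as separate visits: 62/7.54 = 8.2.
- Both adjustments: 50/7.54 = 6.6.

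The range is therefore 6.6 to 10.8.

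**2. What this could do to counts at equal true rates**

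This is an illustration. The assumption is that an event is recorded only if a routine contact falls within D days of it. The documents give no value for D, so a range is shown.

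- Exercise: contacts Monday to Friday, so the gaps g are 1, 1, 1, 1 and 3 days. Capture = Σ min(D, g)/7.
- Control: one contact every 365.25/24 = 15.2 days. Capture = min(1, D/15.2).

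| D (days) | Exercise capture | Control capture | Spurious ratio |
|---|---|---|---|
| 1 | 0.714 | 0.066 | 10.9 |
| 2 | 0.857 | 0.131 | 6.5 |
| 3 | 1.000 | 0.197 | 5.1 |
| 7 | 1.000 | 0.460 | 2.2 |
| 14 | 1.000 | 0.920 | 1.1 |
| 15.2 | 1.000 | 1.000 | 1.0 |

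The model assumes full attendance, no self-report between contacts and no help from the week 4 and 8 visits. Each of these pushes the ratio up, so for a given D the figures lie towards the high end. The ratio exceeds 1 until recall spans the gap between control contacts.

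**The case against.** Several points on the other side stand.

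- **No planned analysis is affected.** Statistics and Sample Size Considerations contains no between-arm comparison of adverse events or medication changes; medications enter only as a covariate. The harm arises only if events are described by arm.
- **Reporting does not depend on scheduled contact alone.** All participants are encouraged to raise problems, and all are told to report biopsy bleeding or wound opening at once. A reader might infer that control events *are* under-recorded. The documents show only a risk, and its size depends on recall and self-report that they do not quantify.
- **Much of the safety experience is found alike in both arms.** Biopsies, local anaesthetic, clamps, glucose tolerance tests, microdialysis, blood draws and exercise tests are common to both, with staff present, and each biopsy has next-day follow-up. A reader might infer that event counts cannot be compared at all. That goes too far: the difficulty is confined to minor events between shared visits.
- **Medication is a minor part.** Recording is required for everyone, and a changed prescription usually persists to the next contact. What remains is that the method and interval of recording are unstated. Likewise, a health change serious enough to end participation would usually still be apparent at the next twice-monthly meeting, so the documents do not support inferring that such exits are distorted by arm.
- **An excess under exercise may be real.** Training injuries can occur only in the arm that trains, so a remedy that discarded events found in training would hide genuine harm.

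These points narrow the concern but do not remove it. The weekly team safety review works on what has already been reported, and the shared contacts could equalise event finding only if the same question were asked at them, which the plan does not provide for.

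**Conclusion.** The concern holds in a limited form. Followed as written, the plan looks for minor and short-lived events about 7 to 11 times more often in the exercise arm, and foot checks and session blood pressures add to the difference. Any by-arm description of such events arising between shared visits would be biased towards more events under exercise. The bias could be about 11-fold if events are noted only within a day, about twofold with a 7-day window, and absent once recall covers the roughly two-week gap in controls.

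The contact ratio follows from the documents; the effect on counts rests on the assumed windows and on ignoring self-report. Serious or lasting events, and events at shared procedures, should be largely unaffected. This is a worthwhile, inexpensive improvement to safety ascertainment and does not threaten the trial's main conclusions.

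**What to change.** At the existing twice-monthly download meetings, at weeks 4 and 8 and at the final visit, ask both arms the same scripted adverse-event question, with a medication update, covering the period since the last meeting. Ask it in full even when an event has already been noted at a training session. Base any by-arm description of non-procedural events on these records.

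Continue to record, act on and fully report events found only at training sessions, foot checks or session blood pressures. Label them by how they were found, so that they are neither mixed into the like-for-like counts nor lost as possible harms of training.

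The cost is a short form at meetings already scheduled, with no added visit. Recall over about two weeks will still miss some trivial events, but both arms would be asked on the same terms.

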Group Assignment Procedure

Following enrollment into the study, participants will be randomized into either the Aerobic Exercise group (n=30) or Control group (n=30. Females and males will be equally distributed between the groups. Regardless of group assignment, each participant will receive standard care for diabetes management.

Aerobic Exercise Training

Every AE training session will be supervised by the research team using established protocols [22-28]. Training sessions will take place at the Central Campus Recreation Building (CCRB), Domino Farms, or other University of Michigan recreation facility (e.g., North Campus Recreation Building) approximately 5 days per week and include treadmill walking, cycling, elliptical, or other related modes of exercise. Briefly, AE training will begin with a 2-week ramp-up, familiarization period of progressing exercise intensity and duration. Training intensity will progress from 55% VO₂max for week 1 (40 min session), to 60-65% VO₂max for week 2 (50 min session), to ~70% VO₂max for all other weeks (50 min session). Subjects will perform a brief warm-up and cool-down (~5 min each) that may include stretching or other light exercises for a total exercise time of 60 min. Subjects will wear heart rate monitors during each training session to provide real-time feedback of target heart rate. Intensity, duration, resting and exercise heart rates, and blood pressures will be recorded for each session. Exercise duration and intensity may be adjusted at the discretion of the PI, Co-I, or study team member. Followup VO₂max tests will be performed at approximately weeks 4 and 8 to monitor progress. AE intensity will be adjusted to match the prescribed training intensity [23, 24, 29-32]. Subjects in the AE training group will also conduct foot safety checks with the research team to monitor foot ulcers/blisters. Relevant findings during foot inspections will be addressed with the participant and study physician. Non-weight bearing exercise may be implemented if the subject is limited.

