EKG: Men may need to have a small amount of chest hair shaved off for the ECG pads to stick correctly. A small amount of adhesive might remain on the skin when the pads are removed or the adhesive might pull on hair when removed.

Exercise: There is a risk of physical injury or fatigue due to the cardiorespiratory fitness test and participation in an exercise intervention. However, these risks are generally considered rare and minor. Our investigation team has extensive experience conducting graded exercise tests in a number of special populations (including elderly and diseased populations) and is well versed in how best to minimize risk during these tests. In addition, exercise testing and training will be performed in a facility equipped with AED devices and staff trained in CPR.

Insulin Clamp Procedure: There is a risk that the subject may react to the infusion of glucose or insulin. These reactions could include low blood sugar, an increase in blood pressure, flushing and/or sweating. In the event one of these reactions occur, medical staff will be notified and appropriate measures will be taken.

Heated Hand Box: There is a minor risk of skin discomfort or burn. If the temperature is too warm it can be reduced to improve comfort.

Oral Glucose Tolerance Test: There is a minor potential risk of reaction to the ingestion of glucose. These reactions could include nausea, low blood sugar, an increase in blood pressure, flushing and/or sweating. Continuous blood glucose monitoring will take place during this procedure to provide real time feedback of glucose levels.

Microdialysis: Inserting the microdialysis probes may be uncomfortable or painful.

Study Diet: It may be burdensome for subjects to adhere to a special diet for an extended period of time. The metabolic kitchen staff at MCRU will work to accommodate participant needs.

Unforeseeable Risks: There may be risks or side effects related to the study that are unknown at this time. Continuous monitoring of all participants will facilitate appropriate action in the event of an unforeseeable risk.

Expected Adverse Reactions

There are no expected adverse events.

Serious Adverse Events and Unanticipated Problems

Subjects will be closely monitored by the research team, MCRU, CVC, and/or Domino Farms staff during all testing procedures. Should a serious event occur, it will be managed promptly by the research team and appropriate medical staff.

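### The stated AED/CPR setting and team presence do not carry over to remote training sessions, and no in-session safeguard is required in their place

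*Combined protocol and SAP*

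**What the plan says.** The general rule under Aerobic Exercise Training is that "Every AE training session will be supervised by the research team using established protocols [22-28", with sessions held at University facilities.

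Two later safety statements carry no exception. The Adverse Events section says "Members of the research team will be present for all components of the study to monitor safety". The Exercise entry under Potential Adverse Events and Mitigation Strategies says "exercise testing and training will be performed in a facility equipped with AED devices and staff trained in CPR".

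The last paragraph under Aerobic Exercise Training opens a different route: "As a contingency, exercise training may be done remotely". At the discretion of the PI, a research team member or the study physician, "participants may conduct exercise training at their residence, local gym, or other appropriate facility". For such a session "a study team member will communicate with the participant prior to the session and discuss the goals and training plan", and that talk covers place, duration, mode and intensity. Contact while the participant is exercising is worded differently: "During the session, a team member may monitor exercise via telephone or video chat (e.g., zoom". Heart rate is captured by a watch and chest strap, stored and downloaded.

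The Exercise entry lists physical injury and fatigue as the risks. Low blood sugar is listed for the insulin clamp and the oral glucose tolerance test, but not for exercise.

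**The concern.** The AED/CPR sentence is offered as the reason why the exercise risk is acceptable. Someone judging risk from the safety sections would conclude that each training session takes place with trained staff and a defibrillator at hand. The contingency paragraph allows a session for which neither is required.

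At stake is the ability to respond. Participants are 40 to 75 years old and have type 2 diabetes, and from week 3 the default prescription is 50 minutes at about 70% of VO2max. A call before the session and a heart-rate file afterwards document the session. They do not put anyone in a position to act if the participant becomes unwell while exercising. The intervention is also defined as supervised training, so whether sessions were supervised bears on whether it was delivered as described.

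**Working it through.** No power, alpha or sample-size figure is involved. The check sets the texts side by side.

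| Protection | Safety sections and general training rule | Remote contingency paragraph |
|---|---|---|
| AED and CPR-trained staff | Stated for all testing and training | Not required |
| Team present or supervising during the session | Stated for every session and all study components | Phone or video contact optional |
| Contact before the session | Not separately stated | Required, including where the session takes place |
| Heart rate | Recorded each session | Recorded by watch and strap, then downloaded |

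**Step 1: the general rule.** The contingency paragraph sits in the same section as the rule that every session is supervised and is labelled a contingency. A specific exception placed there can fairly be read as qualifying that rule, so these two texts need not contradict each other.

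**Step 2: the safety sections.** The presence statement and the AED/CPR statement stand in other sections, mention no remote sessions and refer to no exception. The AED/CPR sentence is the clearer mismatch, because it is specific to training and serves as a mitigation.

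**Step 3: is there a substitute?** The contingency paragraph uses *will* for the call beforehand and *may* for monitoring during the session. It requires no second person, no emergency contact and no AED. The watch gives feedback to the participant; nothing says that staff see the heart rate live. No in-session safeguard is therefore required in place of those given up.

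**Step 4: how long is a session?** From the training prescription, with about 5 minutes each of warm-up and cool-down:
- Week 1: 40 + 5 + 5 = 50 minutes.
- Week 2 onward: 50 + 5 + 5 = 60 minutes.

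This is the time for which live contact is optional in one remote session, and also the staff time needed to make it mandatory. It is not a measure of risk.

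**Step 5: low blood sugar.** All participants have type 2 diabetes, and the Subject Exclusion Criteria name no glucose-lowering drug. The Exercise entry omits low blood sugar, and the routine training record lists no glucose check: "Intensity, duration, resting and exercise heart rates, and blood pressures will be recorded for each session". Reference 22, within the range cited for the training protocols, has exercise-related hypoglycaemia in its title, so the topic is within the plan's own sources.

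**The case against.** The strongest reply is that remote training is a discretionary contingency for people who have already been screened closely. That largely stands:
- Eligibility requires freedom from contraindications to exercise testing or training.
- A physician reviews the ECG, and a graded exercise stress test is done before enrolment.
- The first treadmill bout follows medical clearance and is supervised.
- Intensity and duration can be adjusted, and the team reviews safety weekly.

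These steps lower the chance of an event. They do not provide a response during a session.

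It can also be said that a presence statement covering all components cannot be meant literally, since participants wear a heart-rate watch throughout the study. That is fair, and it is why the AED/CPR sentence carries more of the weight here.

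A third reply is that nothing in the documents shows live contact to be the necessary standard; a companion or a check-in call might do. The choice is partly one of judgement. Live contact is preferred because it keeps the plan's own rule of supervising every session.

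On low blood sugar, precautions may sit in the cited training protocols, which cannot be seen, and diabetes care is left to each participant's own physician. The documents also do not say which drugs participants take. This part is therefore minor.

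**Conclusion.** The point holds as a mismatch between the safety sections and the remote contingency, with no required in-session safeguard to fill the gap. It should be corrected, but it is not a fundamental flaw. It rests on the wording alone and on reading *may* as optional.

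Its size cannot be put in sessions or events, because the documents give no share of remote sessions, no cap and no event rate. No effect on the primary outcome or its analysis is claimed.

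A reader might infer more than the documents support:
- *That remote sessions are unmonitored.* They are not: prior contact is required and heart rate is recorded.
- *That supervision, presence and AED/CPR cover are three separate safeguards, all lost.* Supervision and presence are largely the same thing, so a count of three would double count.
- *That no remote site has an AED.* A local gym may have one; it is only not required.
- *That participants are not told of hypoglycaemia during exercise.* The consent pages are not available, so the point is confined to the risk entry.

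**What to change.** 1. In the contingency paragraph under Aerobic Exercise Training, change *may* to *will*, so that a team member monitors each remote session by phone or video while it takes place. Reschedule if nobody is available.
2. Add an emergency contact to the existing pre-session call, which already covers location.
3. In Adverse Events and in the Exercise entry, limit the presence and AED/CPR statements to on-site sessions, and state the remote safeguards beside them.
4. Record each session as on-site or remote.
5. Minor: name low blood sugar in the Exercise entry, for on-site and remote training alike.

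The cost is protocol wording, one data field and about 50 to 60 minutes of staff time per remote session. That time largely replaces supervision already planned. The plan gives no staff-to-participant ratio, however, so one-to-one contact may take somewhat more than supervision on site. Some remote sessions may be rescheduled or missed, which could press on the expectation that at least 80% of training sessions are completed.
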